
Sample size calculation
	
Justification of the number of subjects
 
This trial is parallel, two-group, with the same size groups.
 
The planned test power is 80% (the probability of making a second kind error is 0.2), the two-way probability of making a type 1 error is 0.05. The sample size was estimated by the main variable of the clinical trial.
 
Thus, this trial was a comparative for superior efficiency.
 
When proving superior therapeutic efficacy, the following statistical hypotheses are tested:
 
H0: e £ d versus On: e > d, where d is the limit of greater efficiency — the marginal value of clinically important differences, at which it can be considered that the tested drug exceeds its effectiveness by control (in this study it was taken equal to 15%); e - estimated (observed) differences between groups in therapeutic efficacy.
 
Given that the main variable is dichotomous, the size of each group can be estimated using the following expressions:
 
n control = k · n main
 $n_{main} = \frac{(z_{\alpha} + z_{\beta})^2}{(\varepsilon - \delta)^2} \cdot \left[\frac{p_{control} \cdot (1 - p_{control})}{k} + p_{main} \cdot (1 - p_{main}) \right]$ 
where: z_{α} and z_{β} —the corresponding percentage points of the standard normal distribution; d - the minimum acceptable value of clinically important differences; e - presumed (observable) differences between groups on therapeutic efficacy (the difference between the shares of positive results in groups); pcontrol and p main —shares of positive results in the

main and control groups, respectively; k - coefficient for unequal number of patients in groups (control is greater than the main); n_{main} и $n_{control}$ - the planned number of patients in the main and control groups, respectively; α is the boundary value of the error of the 1st kind (level of significance); β - is the boundary value of the error of the second kind.

In the planned study, it was assumed that the number of patients in the main and control groups was the same ($k = 1$), the significance level was $\alpha = 0.05$ (two-sided); the boundary value of the error of the second kind is $\beta = 0.2$ (which makes it possible to achieve a research power of 80%). Baseline data and the results of calculations using the above formula are given in Table. 1.

Table 1 - Baseline and Sample Size Estimation Results

Statistical indicator	Value of the indicator
Multiplicity factor k	1

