Boundary probability error of the first kind α	0,025
The probability of an error of the second kind β	0,2
The percentage point S.N.R. for α	1,96
The percentage point S.N.R. for β	0,84
The observed frequency of the positive effect for the control group $p_{control}$	0,75
Estimated value of the positive effect for the main group p_{main}	0,90
The value of the clinically important differences d	0,15
Estimated differences between groups e	0,0
The size of the main group n_{main}	97
The size of the control group $n_{control}$	97
Estimated share of departures	3
Adjusted main group size	100
Adjusted control group size	100

The final number of patients in each group was adjusted for their possible dropout. Thus, the final number of subjects in each group was 100 patients (200 patients in total).

Test treatment	
 - Treatment with Imupret® oral drops according to the respective Summary of Product characteristics (Imupret® coated tablets or oral drops during acute period for 5 days, afterwards switch to the subacute dosage regimen for further 28 days) - Sparing diet; fractional feeding (5-6 times a day) in small portions with the exception of coarse, spicy, heavily digestible foods - Elimination of factors irritating pharyngeal mucosa (thermal, chemical) 
 - As needed, Paracetamol (Acetaminifen) in a single dose of up to 400 mg not more than 3 times daily or paracetamol in a single dose of up to 500 mg 3-4 times daily (if necessary). - Topical agents such as Benzydamine, Lidocaine as needed (in case of severe sore throat). 	
Reference treatment	
 - Sparing diet; fractional feeding (5-6 times a day) in small portions with the exception of coarse, spicy, heavily digestible foods - Elimination of factors irritating pharyngeal mucosa (thermal, chemical) - As needed, Paracetamol (Acetaminifen) in a single dose of up to 400 mg not more than 3 times daily or paracetamol in a single dose of up to 500 mg 3-4 times daily (if necessary). - Topical agents such as Benzydamine, Lidocaine as needed (in case of severe sore throat). 	
Investigational Medicinal Product	Active (add on) treatment	Imupret® oral drops

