8.2 Sample size estimation

The clinical trial is designed in order to obtain a valid description of the in vivo performance of the active (add-on) treatment of Imupret in comparison to the reference standard treatment alone. Endpoints are defined as exploratory endpoints. Depending of the data finally obtained, several exploratory descriptive and statistic evaluations will be performed, so that a biometricaly based sample size estimation is not necessary. However, in order to guarantee a sufficient sample size for exploratory analyses of the data captured, a sample size of N=200 will be included. Treatments will be assorted in a 1:1 ratio, i.e. N=100 will receive an add-on treatment with Imupret® and N=100 will receive the standard treatment only.

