12.2 Statistical evaluation

The statistical planning of the trial and the statistical analyses will be conducted following the principles specified in the ICH Topic E9 (ICH, 1998), and will be carried out by a qualified statistician in accordance with the ICH. Technical details of the statistical analyses will be specified prior to data analyses.

In general, there will be one main statistical evaluation.

Data base will be closed after all data are entered and cleaned.

In general, unless otherwise stated, continuous data will be summarized by means of descriptive statistics (mean, standard deviation (SD), median, quartiles, minimum, and maximum). Categorical variables will be described in contingency tables as absolute number and percentages.

AEs will be evaluated considering frequency and intensity. Furthermore, AEs will be evaluated considering relationship to the IMP, outcome, and seriousness. Both will be described by absolute and relative frequency. Descriptive statistics will be calculated for clinical laboratory parameters determined. Frequencies of values inside and out of normal range (i.e. above and below) will be given where possible.

This is an exploratory trial with no formal sample size estimation. Therefore, beneath descriptive statistics of efficacy endpoints, concluding statistics may be performed in a data driven way, in order to find clinically relevant differences between study participants, time points and treatments. Possible corrections to prevent an alpha inflation will be performed, if meaningful.

Specifications of the biometrical evaluation will be defined after all data management processes of the study phase will be terminated and data base was closed. In general, variables will be analyzed considering the underlying analysis set, treatment and time point, if meaningful.

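### The synopsis tests for a gain above 15 points but assumes a true gain of exactly 15, so power for the stated hypothesis is 2.5%; the claimed 80% holds only against zero difference

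*Protocol*

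**What the plan says.** The Protocol synopsis (section 5, sample size calculation) sets up a superiority-by-margin test: H0 is that e does not exceed d, and the alternative is that e exceeds d. The margin is defined in the phrase "where d is the limit of greater efficiency — the marginal value of clinically important differences", and the text then fixes it as the value "at which it can be considered that the tested drug exceeds its effectiveness by control (in this study it was taken equal to 15" percent. The quantity e is "the difference between the shares of positive results in groups". The section also states: "The planned test power is 80% (the probability of making a second kind error is 0.2"), with a two-sided type 1 error of 0.05.

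Table 1 of the synopsis gives success rates of 0.75 for control and 0.90 for Imupret. Its row "The value of the clinically important differences d" holds 0.15, and its row "Estimated differences between groups e" holds 0.0. The result is 97 per group, raised to 100 for dropout.

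Other sections take a different line. Protocol 8.2 describes exploratory evaluations, "so that a biometricaly based sample size estimation is not necessary". Protocol 12.2 says: "This is an exploratory trial with no formal sample size estimation". The SAP repeats that sentence and names no hypothesis, margin or test.

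**The concern.** Table 1's two success rates differ by 0.15, which is the margin itself. A trial cannot have 80% power to show that a difference exceeds 15 points when the true difference is assumed to be 15 points. The 0.0 entered for e contradicts the rates in the same table, and it is what keeps the formula from dividing by zero.

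There are two ways this can go wrong:

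- **The analyst tests against zero but keeps the synopsis wording.** A significant result could be reported as superiority by a clinically important margin, which the test would not have shown.
- **The analyst runs the test as written.** A product that performs exactly as assumed would almost always fail.

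Nothing in the analysis sections settles which test applies. Protocol 12.2 and the SAP allow data-driven inference and leave the biometrical specifications until after database closure, and the trial is open-label (8.4). The choice of null could therefore be made with results in view.

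**Working it through.** **Inputs** (all from the synopsis text and its Table 1)

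| Quantity | Value |
|---|---|
| Control success rate, pc | 0.75 |
| Imupret success rate, pm | 0.90 |
| Margin d | 0.15 |
| e as defined, pm − pc | 0.90 − 0.75 = 0.15 |
| e as entered in Table 1 | 0.0 |
| Alpha | 0.05 two-sided in the text; 0.025 with z = 1.96 in Table 1 |
| Beta | 0.2, z = 0.84 |
| Allocation k | 1 |
| Allowance for departures | 3 |

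The inequality sign in H0 is garbled in the extracted text and is read here as ≤.

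**1. Reproduce the plan's figure.** The synopsis formula is n = (zα + zβ)² / (e − d)² × [pc(1 − pc)/k + pm(1 − pm)].

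- Variance term: 0.75 × 0.25 + 0.90 × 0.10 = 0.1875 + 0.0900 = 0.2775.
- With Table 1's e = 0.0 and d = 0.15: n = 2.80² / 0.0225 × 0.2775 = 7.84 / 0.0225 × 0.2775 = 96.7, so 97.
- Dropout: 97 / 0.97 = 100, or 97 + 3 = 100. Either reading of the 3 gives 100.

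**2. Use e as the synopsis defines it.** With e = 0.15 and d = 0.15, (e − d)² = 0. No finite n exists.

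**3. Why 97 appears anyway.** (0 − 0.15)² = (0.15 − 0)² = 0.0225. Table 1's entries give the same n as d = 0 and e = 0.15, which is an ordinary test against zero difference.

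**4. Power for the stated hypothesis at 0.75 and 0.90.** Power = Φ((e − d)/SE − 1.96), with SE = √(0.2775/n).

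- n = 97: SE = 0.0535. n = 100: SE = 0.0527.
- (0.15 − 0.15)/SE = 0, so power = Φ(−1.96) = 2.5% at any n.
- Exact binomial enumeration of the same unpooled test: 2.50% at 97 and 2.54% at 100.

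**5. Power against zero at the same rates.**

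- n = 97: Φ(0.15/0.0535 − 1.96) = 80.1%.
- n = 100: Φ(0.15/0.0527 − 1.96) = 81.3%.
- Exact enumeration gives 80.2% and 81.6%. A pooled-variance test gives 79.0% and 80.2%.

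**6. What rejecting the margin null would take.** The observed difference would have to be about 0.15 + 1.96 × 0.0535 = 0.255, or some 25 points. From a control rate near 75%, that means virtually every Imupret patient responding.

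**7. Larger assumed effects** (illustrative; control held at 0.75, Imupret rates not from the documents, unrounded z values). For 80% power to exceed 15 points:

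- Imupret 0.95: 7.849 × (0.1875 + 0.0475) / 0.05² gives 738 per group.
- Imupret 0.99: 7.849 × (0.1875 + 0.0099) / 0.09² gives 192 per group.

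**8. Taking Table 1's e = 0.0 literally as the truth.** Power for the stated hypothesis is Φ(−0.15/0.0535 − 1.96), which is below 0.001%.

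**The case against.** The best defence is that this is a slip in writing up a sound calculation. The e and d rows of Table 1 may simply have been exchanged. With d = 0 and e = 0.15 the formula gives 97, and 100 per group has about 80% power for a plain superiority test. The margin hypothesis appears only in the synopsis; sections 8.1, 8.2 and 12.2 and the SAP call the trial exploratory or decline a formal calculation, so the 2.5% arises only if someone runs the margin test.

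Much of this stands. The sample size is adequate for a test against zero, and the 2.5% is conditional on the hypothesis as written. Over-claiming from a test against zero is probably the more realistic risk.

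It does not remove the problem. Exchanging two table rows is not enough, because the synopsis prose separately sets the margin at 15% and writes it into the null. The exploratory label does not help either: the synopsis states hypotheses, alpha, power and a formula, so the sections that disown a calculation add a second contradiction.

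**Conclusion.** The concern holds. For the hypothesis the synopsis states, at the rates it assumes, power is 2.5% and not 80%, and no increase in sample size changes that. The 80% belongs to a different test, against zero difference, where power is 80.1% at 97 and 81.3% at 100 per group.

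This rests on reading H0 as e ≤ d, on the one-sided 0.025 in Table 1, and on the success rates of 0.75 and 0.90. At a one-sided alpha of 0.05 the figure would be 5%, but that is not what Table 1 uses.

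The fault lies in the hypothesis, the e and d entries and the conflicting statements about whether a calculation exists. It does not lie in the number of patients. It must be corrected because the plan states a power it does not have and leaves the tested null open.

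**What to change.** 1. **Synopsis hypotheses.** Restate as H0: e ≤ 0 against e > 0 at one-sided 0.025, or e = 0 against e ≠ 0 at two-sided 0.05. Use one convention in both text and table.
2. **Table 1.** Set d = 0 and e = 0.15. The results of 97 and, with dropout, 100 per group are unchanged.
3. **Meaning of 15%.** Describe it as the difference the trial is sized to detect. State that a significant result shows superiority, not superiority by at least 15 points.
4. **Sections 8.2 and 12.2 and the SAP.** Either remove the statements that there is no formal calculation and name in the SAP the single primary comparison, its test, analysis set and visit, or keep the trial exploratory and withdraw the 80% claim. The 97 applies to one dichotomous comparison at one time point, whereas Protocol 12.2.2 and the SAP list two main criteria and evaluate scores per visit.
5. **If the 15-point margin is kept as the null,** state the power as 2.5% under the present rates, or justify a larger assumed difference and recalculate.

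The cost of the preferred route is wording in the synopsis, 8.2, 12.2 and the SAP, plus the work of pre-specifying the primary test. It adds no patients. The trial gives up the claim of superiority by 15 points, which it was never sized to support.

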	Mode of administration and dosage regimen	
Imupret® oral drops
 
Dosage for acute symptoms:
 
Children from 6 to 12 years: 15 drops 5-6 times daily
 
Adults and adolescents from the age of 12 years: 25 drops 5-6 times daily
 
Dosage after acute symptoms have subsided:
 
Children from 6 to 12 years: 15 drops 3 times daily
 
Adults and adolescents from the age of 12 years: 25 drops 3 times daily

Duration of treatment	
Disease will be evaluated 36-48 hours prior to active treatment.
 
Active Imupret® treatment group: 10 treatment days
 
Reference treatment group: 10 days
 
Afterwards, there will be a follow up observation phase of 1 months
	

SCHEDULE OF ASSESSMENTS

V1		V2		V3 (Telephone call)					V4	V5
day 1	day 2	day 3	day 4	day 5	day 6	day 7	day 8	day 9	day 10	day 28

Study group 1

Imupret (dosage acute phase)
Reference treatment

Study group 2

Reference treatment

V1	day 1	Screening, randomization, prescription of treatment
V2	day 3	Status evaluation, possible prescription of antibiotics
V3	day 5 ±1	Evaluation of treatment efficacy, telephone call
V4	day 10 ±1	Evaluation of treatment efficacy, end of reference treatment
V5	day 28	Telephone call

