8.3.2 Imupret® oral solution

The composition of the medicinal product is as follows:

Active substances: 100 g drops contain 29 g of an alcoholic aqueous extract (extracting agent: ethanol 59% (V/V) made from the following medicinal plants:

Marshmallow root (Radix Althaeae)	0,4 g;
Camomile flowers (Flores Chamomillae)	0,3 g;
Horstail herb (Herba Equiseti)	0,5 g;
Walnut leaves (Folia Jungladis)	0,4 g;
Yarrow herb (Herba Millefolii)	0,4 g;
Oak bark (Cortex Quercus)	0,2 g;
Dandelion herb (Herba Taraxaci)	0,4 g;

Excipients: Ethanol 19 % (V/V), purified water.

Pharmaceutical form: Oral drops.

Clear or slightly turbid yellow-brown fluid with characteristic taste and chamomile aroma. Turbidity or flocculation may occur during storage.

Name and address of the manufacturer.

Bionorica SE, [name].

Indications. Diseases of the upper respiratory passages (tonsillitis, pharyngitis, laryngitis). Prevention of complications and recurrences in patients with respiratory viral infections caused by the reduced resistance of the organism.

Age	Dosage for acute symptoms	Dosage after acute symptoms have subsided and for prophylactic treatment
Children of 1 year of age	5 drops 5 – 6 times daily	5 drops 3 times daily
Children from 2 to 5 years	10 drops 5 – 6 times daily	10 drops 3 times daily
Children from 6 to 11 years	15 drops 5 – 6 times daily	15 drops 3 times daily
Adults and adolescents from the age of 12 years	25 drops 5 – 6 times daily	25 drops 3 times daily

However, only patients from the age of 6 upwards will be included in the trial.

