Checks for general well-being (AE-checks), checks of restrictions and medication will be performed.

The investigator will estimate indicators for prescription of antibiotics and will decide whether a patient will remain on the study treatment or not. If an antibiotic agent is prescribed, details will be documented and the patient will be instructed about the mode of administration. Intake of

antibiotic drug will be documented in the CRF. Patients with intake of antibiotics will be evaluated separately. At the discretion of the investigator the patient may be advised not to take IMP anymore. If so, this will be documented as well.

Self-assessment of the patient's throat pain by him/herself and (or) his/her parent(s) using a visual analogue scale (VAS) is performed afterwards. Moreover, forms for VAS assessment will be handed over to the patient. The patient will have to assess his/her sore throat every study day until visit 4 on study day 10±1.

10.3 Interim evaluation of treatment efficacy- Visit 3

Visit 3 (V3) will be performed on day 5 ±1 by a telephone call.

Intermediate evaluation of the effectiveness of treatment (day 5-day ±1) via telephone (or visit if necessary); patients self-assessment (VAS; 0-10)

10.4 Treatment efficacy, end of Reference treatment - Visit 4

At visit 4 (V4) on day 10 ±1 the status of the disease will be again evaluated.

A physical examination of vital signs (blood pressure, pulse rate, body temperature (axillar)) will be performed. All physical examinations done at V1 including skin and visible mucosa, palpation of abdomen and lymph nodes, oropharyngoscopy will be repeated to assess the status of the tonsillitis.

Again, objective symptoms included in the "Local Tonsillitis Manifestation Scale".

Checks for general well-being (AE-checks), checks of restrictions and medication will be performed.

Self-assessment of the patient's throat pain by him/herself and (or) his/her parent(s) using a visual analogue scale (VAS; 0-10 points) is performed. Forms of VAS assessment will be collected from the patient.

10.5 Treatment efficacy, end of treatment - Visit 5

Visit 5 (V5) will be performed on day 28 by a telephone call (for both the groups).

Checks for general well-being (AE-checks), checks of restrictions and medication will be performed.

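### The Protocol gives two different triggers for stepping down the Imupret dose, a fixed five days and the subsiding of symptoms, and does not say which governs.

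*Protocol*

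**What the plan says.** The trigger for the dose change appears in three places in the Protocol.

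- Synopsis, Test treatment row: the acute regimen is given "during acute period for 5 days, afterwards switch to the subacute dosage regimen". The trigger is a number of days.
- Synopsis, Mode of administration and dosage regimen: the acute line reads "Children from 6 to 12 years: 15 drops 5-6 times daily". The lower line, under the label "Dosage after acute symptoms have subsided", reads "Children from 6 to 12 years: 15 drops 3 times daily". The trigger is symptom status, with no day.
- Section 8.3.2, product table: the acute column for the youngest eligible children has "15 drops 5 – 6 times daily", and the lower-dose column is headed "Dosage after acute symptoms have subsided and for prophylactic treatment". Again the trigger is symptom status.

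The schedule chart in the synopsis, as it can be read here, labels study group 1 only with "Imupret (dosage acute phase"). Section 10.3 states: "Visit 3 (V3) will be performed on day 5 ±1 by a telephone call". It then allows a visit instead if one is necessary.

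Sections 8.5 and 10.1 to 10.5 describe the visits. Section 10.2 lets the investigator advise a child to stop the study drug, but none of these sections mentions stepping the dose down, defines when acute symptoms count as subsided, or equates the acute period with five days. The SAP does not address the dose regimen.

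**The concern.** The two rules give the same prescription only when a child's symptoms happen to subside on day 5. For other children a site cannot follow both. A child who is well by day 3 is stepped down at once under the symptom rule but stays on the acute dose through day 5 under the calendar rule. A child still ill on day 6 stays on the acute dose under the symptom rule but has already been stepped down under the calendar rule.

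Three parts of the plan need one prescribed dose for each day:

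- therapy compliance, listed among the secondary variables in the synopsis;
- withdrawal for poor compliance (Protocol section 9.4.1);
- exclusion from the per-protocol set for major deviations (Protocol section 12.2.1 and SAP, Analysis sets).

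Without a single rule, the same record of intakes can be full compliance at one site and a shortfall at another, and the report cannot state exactly which regimen was tested.

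**Working it through.** The documents state no daily total, course total or ratio, so there is no figure of theirs to reproduce. The size follows from the dosage lines.

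**Inputs**

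- Drops per intake: 15 (synopsis dosage row; section 8.3.2).
- Intakes per day: f = 5 or 6 at the acute dose, 3 at the lower dose (same places).
- Calendar switch: after day 5 (synopsis, Test treatment).
- Course length: 10 days, taken as an assumption. The synopsis (Duration of treatment) and section 8.5 both give 10 days, but the Test treatment sentence speaks of a further 28 days after the switch.

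**Daily dose on a day when the rules disagree**

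- Acute: 15 × 5 = 75 to 15 × 6 = 90 drops.
- Lower: 15 × 3 = 45 drops.
- Ratio: 75/45 = 1.67 to 90/45 = 2.00.

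The 25-drop row gives the same ratio: 125 to 150 against 75 drops. The daily ratio does not depend on the course length.

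**Ten-day total when day k is the last day on the acute dose**

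Total = 15 × f × k + 45 × (10 − k). The comparison is with k = 5 at the same f, so that the permitted range of 5 to 6 intakes is not counted as an effect of the trigger.

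| Last acute day | f = 5 | f = 6 | Change from calendar rule |
|---|---|---|---|
| 2 (early recovery) | 150 + 360 = 510 | 180 + 360 = 540 | 510/600 = 0.85; 540/675 = 0.80 |
| 3 | 225 + 315 = 540 | 270 + 315 = 585 | 0.90; 0.87 |
| 5 (calendar rule) | 375 + 225 = 600 | 450 + 225 = 675 | reference |
| 7 | 525 + 135 = 660 | 630 + 135 = 765 | 1.10; 1.13 |
| 10 (symptomatic throughout) | 750 | 900 | 750/600 = 1.25; 900/675 = 1.33 |

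The last row follows from the symptom rule for a child who is ill to day 10 and does not need the chart.

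**Effect on compliance**

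Take a child still symptomatic on day 6 who has 3 intakes. Under the calendar rule that is 3/3 = 100% of the prescribed intakes. Under the symptom rule it is 3/6 = 50% to 3/5 = 60%.

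**The case against.** The strongest reply is that the two statements can be read together. The Test treatment parenthesis would then define the acute period for this trial as five days, the dosage row would only give the drops for each phase, and section 8.3.2 would be product description, since it also covers one-year-olds, adults and prophylaxis. That reading is possible, but no passage states it, and the dosage row uses symptom status alone. The parenthesis may also be leftover text: it mentions tablets, and its further 28 days do not fit a 10-day course. Even so, it stands in the row that defines the test treatment and needs correcting.

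Other objections do stand, and they rule out stronger readings that a reader might infer:

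- **The chart as a third rule.** It names only the acute dosage, but bars or shading may have been lost when the PDF was read. It is something to check, not evidence.
- **A 1.76-fold range in total exposure.** Dividing 900 by 510 gives 1.76, but it pairs six intakes with five and a slow recoverer with a fast one. For the same child at equal frequency, the totals differ from the calendar rule by at most a third.
- **No examination between days 3 and 10.** V3 can become a visit, and section 8.5 allows unscheduled visits. Whether tonsillar signs are needed to judge that symptoms have subsided is not stated.
- **A regimen that does differ by site.** The documents show only that it can.
- **A biased treatment comparison.** Under the symptom rule dose would follow response, which would confound an exposure-response analysis, but neither document plans one. The randomised contrast of add-on against reference treatment is unaffected, and the scheduled antibiotic decision at V2 (day 3) comes before the calendar switch.

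Therapy compliance is also absent from the secondary endpoints in Protocol section 12.2.3 and the SAP, which limits its weight as an endpoint. The withdrawal and per-protocol decisions still need a reference dose.

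**Conclusion.** The contradiction is in the current text and rests on the two synopsis rows and the product table. It is a conflict between stated rules, not a missing detail.

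Its size is a 1.67 to 2.0-fold difference in prescribed daily dose on each day when the rules disagree. The difference in the 10-day total at equal intake frequency is about -15% to -20% for a child well after 2 days and +25% to +33% for a child symptomatic throughout. These totals assume a 10-day course, one age row and intakes taken as prescribed; the 2-day and 10-day recoveries are illustrations, not forecasts.

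The harm is limited to the definition of the regimen, the synopsis compliance variable, and the compliance-withdrawal and per-protocol decisions. It does not invalidate the randomised comparison in the full analysis set. The point should be corrected, but it does not undermine the trial.

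**What to change.** - Reconcile the Test treatment row, the synopsis dosage row and section 8.3.2 into one switch rule for all sites, and check the original schedule chart against it. The choice of rule is the sponsor's, and none is proposed here.
- State at which contact the rule is applied and by whom. If it rests on symptoms, define when they count as subsided.
- Record the date of the dose change and the doses taken each day, if the CRF or patient form does not already do so (neither is among the documents). The record must start at V1; the daily VAS forms are handed out only at V2 (section 10.2).
- Compute therapy compliance, and judge poor compliance and per-protocol deviations, against that one rule.
- In the same edit, reconcile two neighbouring contradictions that are separate from this point: the further 28 days against 10 treatment days, and age 12, which falls in both synopsis dosage lines while the child row in section 8.3.2 ends at 11.

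The cost is Protocol wording and at most two recorded items, with a form issued from V1 if none exists. No extra visits or patients are needed.

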8.5 Time schedule and visits

Four scheduled visits will be performed during the first phase of the study:

First study phase

- 1 visit (1st day): screening, randomization and treatment; evaluation by Mc Isaac Score scale; LTM Scale (Local Tonsillitis Manifestation Scale): (5 symptoms: Sore throat at swallowing (0 – absent, 1 – mild, 2 – moderate, 3 – severe / pronounced); Sore throat at rest; Throat irritation at rest; Palatine tonsils hyperemia; Palatine tonsils edema); Patients self-assessment (VAS; 0-10)

- 2 visit (3rd±1 day): intermediate evaluation of the effectiveness of treatment - clarification of the patient's condition, the need to prescribe an antibiotic; evaluation by LTM Scale, patients self-assessment (VAS; 0-10)
- 3 visit: intermediate evaluation of the effectiveness of treatment (day 5-day ±1) via telephone (or visit if necessary); patients self-assessment (VAS; 0-10)
- 4 visit: final (10th day ±1 day). Evaluation by LTM Scale (0-15), patients self-assessment (VAS; 0-10)
- 5 Follow up; day 28: evaluation of the long-term effects of treatment
- - An unscheduled visit can be made if the patient's condition worsens (according to the patient and / or the researcher, including if the symptoms of the disease persist or worsen, including but not limited to an increase in the temperature in the armpit above 38.0 ° C at the 3rd and / or subsequent days of treatment).
- The total duration of the treatment: 10 days
- The total duration of the study for one patient is not longer than 38 days.

Any unscheduled visit may be carried out in case of worsening of the patient's condition (at patient's and/or investigator's opinion), including persistence or aggravation of the disease symptoms.

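### The protocol states the Imupret course as 33 days in one place and 10 in others, with two switch rules and a last contact that does not match the promised follow-up

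*Protocol*

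**What the plan says.** Course length:

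- Protocol synopsis, Test treatment: "oral drops during acute period for 5 days", then "afterwards switch to the subacute dosage regimen for further 28 days". This stands in a parenthesis that follows a reference to the Summary of Product Characteristics.
- Protocol synopsis, Duration of treatment: "Active Imupret® treatment group: 10 treatment days".
- Protocol section 8.5: "The total duration of the treatment: 10 days".
- Protocol section 10.5, on the day-28 telephone call, is headed "Treatment efficacy, end of treatment - Visit 5". Section 10.4 heads Visit 4 (day 10 ±1) as the end of the reference treatment only and does not say that Imupret stops there.

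Switch to the lower dosage: the Test treatment row places it after 5 days. The synopsis dosage row and the table in section 8.3.2 place it after acute symptoms have subsided. The schedule of assessments labels the active arm "Imupret (dosage acute phase".

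Follow-up: the Duration of treatment row adds "Afterwards, there will be a follow up observation phase of 1 months". The schedule, section 8.5 and section 10.5 all place the last contact on day 28. Section 8.5 adds "The total duration of the study for one patient is not longer than 38 days". Section 11.2 collects adverse events from consent to the end of the trial, follow-up included, without naming a day.

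The SAP gives neither a treatment duration nor a follow-up length.

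**The concern.** Two sites could each follow the protocol faithfully and still give the study drug for different lengths of time. One working from the Test treatment row would continue well past the end of treatment in section 8.5, and part of that dosing would fall after the last scheduled safety contact.

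Several parts of the plan need a single reference regimen. Therapy compliance is a secondary variable in the synopsis. Poor compliance is a reason for withdrawal (section 9.4.1). Membership of the per-protocol set depends on protocol deviations (section 12.2.1). Imupret is handed over at Visit 1 (section 10.1), so the quantity supplied depends on the duration. Without one stated end of treatment, an adverse event on, say, day 20 cannot be classed as on or off treatment by rule.

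The switch rule matters separately, because it can change what a child takes before the final efficacy visit on day 10.

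**Working it through.** **Inputs.** Acute phase 5 days and subacute phase 28 days (synopsis, Test treatment). Course of 10 days (synopsis, Duration of treatment; section 8.5). Last contact on day 28 (schedule; sections 8.5 and 10.5). Cap of 38 days (section 8.5). Dosage for children of 15 drops, 5–6 times daily in the acute phase and 3 times daily afterwards (synopsis dosage row; section 8.3.2).

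**Assumptions.** The first dose is on day 1. One month is taken as 28 to 31 days, since the protocol does not define it. Drop totals use 15 drops per dose; a 12-year-old on the 25-drop line would have higher totals.

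**Step 1: course length.** The 10 days of section 8.5 cannot be obtained from the Test treatment row: 5 + 28 = 33 days. The difference is 33 − 10 = 23 days, a ratio of 33/10 = 3.3. A 10-day course that switches after day 5 leaves 10 − 5 = 5 subacute days, not 28.

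**Step 2: follow-up under each possible end of treatment.**

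| Reading | Last treatment day | Day 28 minus last treatment day | One month later (+28 to +31) | Within 38 days? |
|---|---|---|---|---|
| 10 days | 10 | +18 | day 38 to 41 | only with a 28-day month |
| To Visit 5 (heading of 10.5) | 28 | 0 | day 56 to 59 | no |
| 33 days | 33 | −5 | day 61 to 64 | no |

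Under the 10-day reading, the scheduled follow-up is 18 days rather than a month. Under the 33-day reading, the call comes 5 days before the course ends. Under the heading of section 10.5, no scheduled contact off treatment remains.

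**Step 3: the switch rule.** Daily intake is 15 × 5 = 75 to 15 × 6 = 90 drops in the acute phase and 15 × 3 = 45 drops after it. A child still symptomatic after day 5 would take 75–90 drops a day on days 6 to 10 under the symptom rule, and 45 under the 5-day rule. Over those 5 days that is 375–450 drops against 225.

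**Step 4: total exposure at 15 drops per dose.**

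| Course | Total drops |
|---|---|
| 10 days, acute dosage throughout | 10 × 75 = 750 to 10 × 90 = 900 |
| 5 acute + 5 subacute days | 375 + 225 = 600 to 450 + 225 = 675 |
| 5 acute + 28 subacute days | 375 + 1,260 = 1,635 to 450 + 1,260 = 1,710 |

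**Step 5: what is the same up to day 10.** The last scheduled symptom assessment is Visit 4, on day 10 ±1. Section 10.5 lists only well-being, restriction and medication checks at Visit 5. A 10-day and a 33-day course that both switch after day 5 give the same dosing through day 10. Total length alone therefore leaves the day-10 comparison unchanged; only a different switch rule can alter exposure before it.

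**The case against.** The best defence is that the two statements written specifically about duration agree on 10 days. The 33-day figure occurs once, in a parenthesis about the product information that also mentions coated tablets, although the trial product is oral drops. It may be carried-over label text. The heading of section 10.5 may be residue too, since the table of contents still lists Visits 6 to 8. This is plausible, but the parenthesis stands in the row that defines the test arm and nothing marks it as background. No passage says which statement governs.

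A reader might infer four stronger things that the documents do not support:

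- **That the safety window is undefined.** Section 11.2 defines it in words and requires events to be followed until they subside or stabilise, and section 11.3 also records events volunteered between visits. Only the calendar end is unclear.
- **That the 38-day cap is a further contradiction.** It is an upper limit. Day 28 lies below it, and 10 + 28 = 38 meets it exactly. What it cannot hold is a 33-day course plus a month. The day-28 entry in section 8.5 might even be read as day 28 of follow-up, but the schedule's day row and section 10.5 point to study day 28.
- **That the schedule prescribes the acute dosage throughout.** The extent of the treatment bar is lost in the available text, so the label cannot show how many days it covers. The 750–900 drop total is therefore a possible exposure, not a stated one.
- **That the efficacy result cannot be tied to a regimen.** Course length alone does not change dosing before day 10. Some variation between children is also intended under a symptom-based switch and a range of 5–6 doses daily.

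**Conclusion.** The inconsistency is real, and neither document resolves it. The stated course is 33 or 10 days, a difference of 23 days, and a section heading points to day 28 as a third end of treatment. The switch is either at 5 days or symptom-based, which at 15 drops per dose can mean 75–90 or 45 drops a day on days 6 to 10. The promised month of follow-up after 10 treatment days would end on day 38 to 41, but the last scheduled contact is day 28.

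The consequences lie mainly in exposure after day 10, compliance, per-protocol status, drug supply and the on- or off-treatment status of adverse events. The day-10 efficacy comparison is touched only through the switch rule. The day counts assume dosing from day 1 and a month of 28 to 31 days; the 10-versus-33-day conflict depends on neither. The documents do not show which duration or switch rule was intended.

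**What to change.** Reconcile the synopsis (Test treatment, dosage and Duration of treatment rows, and the schedule) with sections 8.3.2, 8.5, 10.5 and 11.2, so that they state:

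- one Imupret duration;
- one rule for the switch to the lower dosage;
- one last safety contact, given as a study day and consistent with the end of treatment, the follow-up length and the 38-day cap.

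Retitle section 10.5 to match. If the parenthesis in the Test treatment row is only a summary of the product information, say so or remove it. Which duration and which switch rule apply is for the sponsor's clinicians.

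The cost is protocol wording, or at most moving one telephone call.
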